
 
• To assess protocol specified AESIs, medically-attended adverse events (MAAEs), including new-onset chronic medical conditions (NOCMCs) and potentially immune-mediated medical conditions (PIMMCs) that occur after receipt of study product.
 
	
 
• Occurrence of all protocol specified AESIs, MAAEs, including NOCMCs and PIMMCs, from the time of the first study vaccination through approximately 12 months following the first vaccination.
 

Secondary Immunogenicity Objectives
	
Secondary Immunogenicity Outcome Measures

 
• To assess the HAI, Neut and NAI ELLA responses to the 2019/2020 QIV strains prior to (Day 1) and approximately 28 days after vaccination with the 2019/2020 QIV in all study groups
 
	
 
• The percentage of subjects achieving an HAI titer <math>\geq 1:40</math> against 2019/2020 QIV strains approximately on Days D90 (baseline) and D118 (28 days post-2019/2020 vaccine) for each study group.
 
• The percentages of subjects achieving HAI, Neut and NAI titer seroconversion, against 2019/2020 QIV strains on
 

	
approximately Day 118 for each study group (NAI titers will only be assessed on study groups 1,2 and 3).
 
 
• Serum Neut, HAI and NAI GMTs against 2019/2020 QIV strains approximately on Days D90 (baseline) and D118 (28 days post-2019/2020 QIV) for each study group (NAI titers will only be assessed on study groups 1,2 and 3).
 
• Ratio of serum Neut, HAI and NAI GMTs against 2019/2020 QIV strains between adjuvanted and unadjuvanted study groups approximately on Days D90 (baseline) and D118 (28 days post-2019/2020 QIV). NAI titers will only be assessed on study groups 1,2 and 3.
 
• Serum Neut, HAI and NAI GMFRs against 2019/2020 QIV strains from baseline (D90) on approximately D118 for each study group (NAI titers will only be assessed on study groups 1,2 and 3).
 

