
 
• To assess the influenza neutralizing (Neut) antibody titer responses against heterologous influenza A/H1 and H3 strains from baseline (Day 1) to approximately Days 8,
 
	
 
• The percentage of subjects achieving Neut titer seroconversion against heterologous H1 and H3 influenza strains
 

29, 57, 90, and 118 after administration of 2018/2019 Fluzone and Flublok with and without AF03 or Advax-CpG55.2 adjuvant.
	
on approximately Days 8, 29, 57, 90, and 118 for each study group.
 
 
• Serum Neut GMT against heterologous H1 and H3 influenza strains at baseline (Day 1) and approximately Days 8, 29, 57, 90, and 118 for each study group.
 
• Ratio of serum Neut GMT against heterologous H1 and H3 influenza strains between adjuvanted and unadjuvanted study groups at baseline (Day 1) and approximately Days 8, 29, 57, 90, and 118.
 
• Geometric mean fold rise (GMFR) of neut antibody titers from baseline against heterologous H1 and H3 influenza strains at baseline (Day 1) and approximately Days 8, 29, 57, 90, and 118 for each study group.
 

 
• To assess the longitudinal kinetics and durability of the HAI, NAI, and Neut responses against the 2018/2019 QIV strains on approximately Days 8, 57, 90, and 118 following receipt of the 2018/2019 Fluzone and Flublok with and without AF03 or Advax-CpG55.2 adjuvant.
 
	
 
• The percentage of subjects achieving HAI, NAI and Neut titer seroconversion against 2018/2019 QIV antigens and strains on approximately Days 8, 57, 90, and 118 for each study group (NAI titers will only be assessed on study groups 1,2 and 3).
 
• The percentage of subjects achieving an HAI and Neut titer <math>\geq 1:40</math> against 2018/2019 QIV strains on approximately Days 8, 57, 90, and 118 for each study group (NAI titers will only be assessed on study groups 1,2 and 3).
 
• Serum Neut, HAI and NAI GMT against 2018/2019 QIV strains on approximately Days 8, 57, 90, and 118 for each study group (NAI titers will only be assessed on study groups 1,2 and 3).
 

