	
 
• Ratio of serum Neut, HAI and NAI GMT against 2018/2019 QIV strains between adjuvanted and unadjuvanted study groups on approximately Days 8, 57, 90, and 118 (NAI titers will only be assessed on study groups 1,2 and 3).
 
• Geometric mean fold rise (GMFR) in HAI, Neut and NAI titers from baseline (Day 1) against the 2018/2019 QIV strains at approximately Day 8, 57, 90, and 118 for each study group (NAI titers will only be assessed on study groups 1,2 and 3).
 

Exploratory Immunogenicity Objectives
	
Exploratory Immunogenicity Study Outcomes

 
• To assess the HAI antibody responses against heterologous influenza A/H1 and H3 strains from baseline (Day 1) to approximately Days 180 and 365 after receipt of 2018/2019 Fluzone or Flublok with and without AF03 or Advax-CpG55.2 adjuvant.
 
	
 
• The percentages of subjects achieving HAI titer seroconversion, against heterologous H1 and H3 influenza strains on approximately Days 180 and 365 for each study group.
 
• The percentage of subjects achieving an HAI titer <math>\geq 1:40</math> against heterologous H1 and H3 influenza strains at baseline (Day 1) and approximately Days 180 and 365 for each study group.
 
• Serum HAI GMT against heterologous H1 and H3 influenza strains at baseline (Day 1) and approximately Days 180 and 365 each study group.
 
• Ratio of serum HAI GMT against heterologous H1 and H3 influenza strains between adjuvanted and unadjuvanted study groups at baseline (Day 1) and approximately Days 180 and 365.
 
• Geometric mean fold rise (GMFR) in HAI from baseline (Day 1) against heterologous H1 and H3 influenza strains
 

	
at approximately Days 180 and 365 for each study group

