
 
• To assess the longitudinal kinetics and durability of the HAI, NAI, and Neut responses against the 2018/2019 QIV strains on approximately Days 180 and 365 following receipt of the 2018/2019 Fluzone and Flublok with and without AF03 or Advax-CpG55.2 adjuvant.
 
	
 
• The percentage of subjects achieving HAI, NAI and Neut titer seroconversion against 2018/2019 QIV antigens and strains on approximately Days 180 and 365 for each study group (NAI titers will only be assessed on study groups 1,2 and 3).
 
• The percentage of subjects achieving an HAI and Neut titer <math>\geq 1:40</math> against 2018/2019 QIV strains on approximately Days 180 and 365 for each study group (NAI titers will only be assessed on study groups 1,2 and 3).
 
• Serum Neut, HAI and NAI GMT against 2018/2019 QIV strains on approximately Days 180 and 365 for each study group (NAI titers will only be assessed on study groups 1,2 and 3).
 
• Ratio of serum Neut, HAI and NAI GMT against 2018/2019 QIV strains between adjuvanted and unadjuvanted study groups on approximately Days 180 and 365 (NAI titers will only be assessed on study groups 1,2 and 3).
 
• Geometric mean fold rise (GMFR) in HAI, Neut and NAI titers from baseline (Day 1) against the 2018/2019 QIV strains at approximately Day 180 and 365 for each study group (NAI titers will only be assessed on study groups 1,2 and 3).
 

 
• To assess the HAI, Neut and NAI ELLA responses to the 2018/2019 at all timepoints and 2019/2020 QIV strains prior to and
 
	
 
• The percentage of subjects achieving an HAI titer <math>\geq 1:40</math> against 2018/2019 QIV strains at all timepoints and against 2019/2020 QIV strains at approximately D90 and D118.
 

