**Description of Study Design:**

This is a Phase I, randomized, double blinded, clinical trial in up to 240 males and non-pregnant females, 18-45 years of age, inclusive, who are in good health and meet all eligibility criteria. This clinical trial is designed to assess the safety, reactogenicity and immunogenicity of either the 2018/2019 Fluzone or Flublok Quadrivalent Influenza Vaccines (QIV), manufactured by Sanofi Pasteur (SP) given without adjuvant or with one of two adjuvant formulations, AF03 (SP) or Advax-CpG55.2 (Vaxine Pty Ltd). Fluzone is a quadrivalent split virion inactivated vaccine whereas Flublok is a quadrivalent influenza vaccine that contains recombinant hemagglutinin proteins. AF03 is a squalene-based emulsion adjuvant, whereas Advax-CpG55.2 is a combination adjuvant comprised of delta inulin and the oligonucleotide, CpG55.2. Enrollment will occur in the second and third quarters of calendar year 2019 to allow antibody titers to previous doses of 2018/2019 IIV to wane.

Subjects will be stratified by prior receipt of licensed, seasonal influenza vaccine (defined as receipt of at least one of the 2017/2018 and/or 2018/2019 influenza vaccines) and will be randomly assigned to 1 of 6 treatment arms to receive a single dose of one of the two seasonal 2018/2019 QIV vaccine formulations with or without one of the two adjuvants (Day 1). On approximately Day 90, each subject will receive a single dose of the seasonal 2019/2020 influenza vaccine. Groups 1, 2 and 3 will receive 2019/2020 Fluzone QIV and Groups 4, 5 and 6 will receive 2019/2020 Flublok QIV.

To determine early safety signals for this Phase I study, enrollment will proceed in a staged fashion for the first 6 sentinel subjects. The first six subjects will be randomized and vaccinated with one each from Groups 1-6. These six subjects will be followed through Day 8. If any of the pre-specified halting rules for the sentinel subjects occur, the study will be halted and reviewed by the DSMB. If no pre-specified safety signals are encountered enrollment will proceed.

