## **2.2 Scientific Rationale**

Seasonal influenza vaccines have variable efficacy. Efficacy can be reduced when the vaccine strains have mismatched antigenic profiles as compared to the circulating strains of influenza virus. Additionally, populations can have variable efficacy based on the immunological sequence of prior exposure to influenza infections or vaccines. Adjuvants provide a promising strategy to enhance the humoral immune responses to influenza proteins and may enhance the cellular memory responses, as well. Two new adjuvants are being evaluated that show promise in animal studies (Advax-CpG55.2 and AF03) and early human trials (AF03). These two products have been tested predominantly as adjuvants for novel avian influenza strains that show poor immunogenicity. However, there is great need to improve vaccine efficacy that can overcome the problems of antigenic drift, immunosenescence and prior immunological priming.

The goal of this clinical trial is to assess in healthy adults, 18-45 years of age, the safety, reactogenicity and immunogenicity of one dose of 2018/2019 Quadrivalent Influenza Vaccine (either Fluzone or Flublok) administered intramuscularly (IM) with or without one of two adjuvants (AF03 or Advax-CpG55.2). The study will evaluate the traditional HAI and Neut

responses among groups, but also will explore additional immunological parameters. Since antibodies targeting the NA may represent an independent correlate of protection against influenza infection [43] [5], we plan to assess the NAI responses in each group. The longitudinal kinetics and durability of HAI, Neut, and NAI responses will be evaluated for one year following vaccination.

This clinical trial will also assess cellular correlates of immunity to influenza including memory B cell populations, plasmablasts, TFH cells, functional non-neutralizing Fc-effector antibodies, as well as determine the transcriptional profiling responses following vaccination.

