2.1. Purpose of the Analyses

These analyses will assess the safety and immunogenicity of one dose of 2018/2019 Quadrivalent Influenza Vaccine (either Fluzone or Flublok) administered IM with or without one of two adjuvants (AF03 or Advax-CpG55.2) and will be included in the expedited report and clinical study report.

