GMT (95% CI)	xxx.x (xxx.x,xxx.x)	xxx.x (xxx.x,xxx.x)	xxx.x (xxx.x,xxx.x)	xxx.x (xxx.x,xxx.x)	xxx.x (xxx.x,xxx.x)	xxx.x (xxx.x,xxx.x)
Ratio of GMTs (95% CI) ^a	-	xx.x (xx.x,xx.x)	xx.x (xx.x,xx.x)	-	xx.x (xx.x,xx.x)	xx.x (xx.x,xx.x)
Seroconversion - % (95% CI)	xx (xx, xx)	xx (xx, xx)	xx (xx, xx)	xx (xx, xx)	xx (xx, xx)	xx (xx, xx)
Titer ≥ 1:40 - % (95% CI)	xx (xx, xx)	xx (xx, xx)	xx (xx, xx)	xx (xx, xx)	xx (xx, xx)	xx (xx, xx)
GMFR (95% CI)	xx.x (xx.x,xx.x)	xx.x (xx.x,xx.x)	xx.x (xx.x,xx.x)	xx.x (xx.x,xx.x)	xx.x (xx.x,xx.x)	xx.x (xx.x,xx.x)
Day 90 Post Vaccination 1						
n	x	x	x	x	x	x
GMT (95% CI)	xxx.x (xxx.x,xxx.x)	xxx.x (xxx.x,xxx.x)	xxx.x (xxx.x,xxx.x)	xxx.x (xxx.x,xxx.x)	xxx.x (xxx.x,xxx.x)	xxx.x (xxx.x,xxx.x)
Ratio of GMTs (95% CI) ^a	-	xx.x (xx.x,xx.x)	xx.x (xx.x,xx.x)	-	xx.x (xx.x,xx.x)	xx.x (xx.x,xx.x)
Seroconversion - % (95% CI)	xx (xx, xx)	xx (xx, xx)	xx (xx, xx)	xx (xx, xx)	xx (xx, xx)	xx (xx, xx)
Titer ≥ 1:40 - % (95% CI)	xx (xx, xx)	xx (xx, xx)	xx (xx, xx)	xx (xx, xx)	xx (xx, xx)	xx (xx, xx)
GMFR (95% CI)	xx.x (xx.x,xx.x)	xx.x (xx.x,xx.x)	xx.x (xx.x,xx.x)	xx.x (xx.x,xx.x)	xx.x (xx.x,xx.x)	xx.x (xx.x,xx.x)
Day 118 Post Vaccination 1						
n	x	x	x	x	x	x
GMT (95% CI)	xxx.x (xxx.x,xxx.x)	xxx.x (xxx.x,xxx.x)	xxx.x (xxx.x,xxx.x)	xxx.x (xxx.x,xxx.x)	xxx.x (xxx.x,xxx.x)	xxx.x (xxx.x,xxx.x)
Ratio of GMTs (95% CI) ^a	-	xx.x (xx.x,xx.x)	xx.x (xx.x,xx.x)	-	xx.x (xx.x,xx.x)	xx.x (xx.x,xx.x)
Seroconversion - % (95% CI)	xx (xx, xx)	xx (xx, xx)	xx (xx, xx)	xx (xx, xx)	xx (xx, xx)	xx (xx, xx)
Titer ≥ 1:40 - % (95% CI)	xx (xx, xx)	xx (xx, xx)	xx (xx, xx)	xx (xx, xx)	xx (xx, xx)	xx (xx, xx)
GMFR (95% CI)	xx.x (xx.x,xx.x)	xx.x (xx.x,xx.x)	xx.x (xx.x,xx.x)	xx.x (xx.x,xx.x)	xx.x (xx.x,xx.x)	xx.x (xx.x,xx.x)
Day 180 Post Vaccination 1						
n	x	x	x	x	x	x

Time Point	Group 1 Fluzone (N=X)	Group 2 Fluzone + AF03 (N=X)	Group 3 Fluzone + Advax- CpG (N=X)	Group 4 Flublok (N=X)	Group 5 Flublok + AF03 (N=X)	Group 6 Flublok + Advax- CpG (N=X)
GMT (95% CI)	xxx.x (xxx.x,xxx.x)	xxx.x (xxx.x,xxx.x)	xxx.x (xxx.x,xxx.x)	xxx.x (xxx.x,xxx.x)	xxx.x (xxx.x,xxx.x)	xxx.x (xxx.x,xxx.x)
Ratio of GMTs (95% CI) ^a	-	xx.x (xx.x,xx.x)	xx.x (xx.x,xx.x)	-	xx.x (xx.x,xx.x)	xx.x (xx.x,xx.x)
Seroconversion - % (95% CI)	xx (xx, xx)	xx (xx, xx)	xx (xx, xx)	xx (xx, xx)	xx (xx, xx)	xx (xx, xx)
Titer ≥ 1:40 - % (95% CI)	xx (xx, xx)	xx (xx, xx)	xx (xx, xx)	xx (xx, xx)	xx (xx, xx)	xx (xx, xx)

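### Durability of the 2018/2019 vaccine response is an objective at Days 118, 180 and 365, but every group is due 2019/2020 vaccine at about Day 90, so those days describe the two-vaccination sequence and not persistence of the first dose.

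*Protocol*

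**What the plan says.** Protocol Table 1, repeated in SAP 3.1, sets this secondary objective for the period after the 2018/2019 vaccine: "longitudinal kinetics and durability of the HAI, NAI, and Neut responses against the 2018/2019 QIV strains on approximately Days 8, 57, 90, and 118". Its outcomes include fold rise in "titers from baseline (Day 1) against the 2018/2019 QIV strains at approximately Day 8, 57, 90, and 118". An exploratory objective extends this to later days: "longitudinal kinetics and durability of the HAI, NAI, and Neut responses against the 2018/2019 QIV strains on approximately Days 180 and 365". Protocol 2.2, with the same sentence in SAP 2, adds: "The longitudinal kinetics and durability of HAI, Neut, and NAI responses will be evaluated for one year following vaccination". SAP 2.1 states the purpose in terms of the first vaccine only: "These analyses will assess the safety and immunogenicity of one dose of 2018/2019 Quadrivalent Influenza Vaccine".

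The design section says: "On approximately Day 90, each subject will receive a single dose of the seasonal 2019/2020 influenza vaccine". Protocol Table 2 shows this for all six groups. For the 2019/2020 strains, Table 1 itself describes the same visit as "D118 (28 days post-2019/2020 vaccine) for each study group".

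SAP 3.2 takes fold rise from Day 1, except for results against 2019/2020 strains, where the baseline is Day 90. The shells for 2018/2019 strains (Table 21 and those built on the same pattern) carry rows such as "Day 118 Post Vaccination 1", with GMT, seroconversion and GMFR, and the same for Days 180 and 365.

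**The concern.** A reader of the study report would take the Day 118, 180 and 365 results for 2018/2019 strains as showing how long the first, possibly adjuvanted, vaccination lasts. That is what the objectives say they are for. A second influenza vaccination given before all three days can raise the titers, and no randomized arm is left without it to separate persistence from boosting. Neither document limits the durability objective to earlier samples or attributes the later rows to both vaccinations. At stake is the descriptive durability conclusion for each adjuvant, including in the topline tables that go to DMID and the manufacturer (SAP 6.2.2).

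**Working it through.** **Timing.** Inputs are the visit days and windows in Protocol 8.2 and 8.3. The protocol's own interval reproduces: 118 − 90 = 28 days. Likewise 180 − 90 = 90 and 365 − 90 = 275. Across the windows (second dose Day 76 to 104):

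| Visit | Shortest gap | Longest gap |
|---|---|---|
| Day 118 (115 to 121) | 115 − 104 = 11 | 121 − 76 = 45 |
| Day 180 (166 to 194) | 166 − 104 = 62 | 194 − 76 = 118 |
| Day 365 (351 to 400) | 351 − 104 = 247 | 400 − 76 = 324 |

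All three days follow the second dose under every scheduled window. That is 1 of 4 secondary durability days and 2 of 2 exploratory ones.

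**Share of the year before the second dose.** (90 − 1)/(365 − 1) = 89/364 = 24.5%. With the second dose on Day 76 it is 75/364 = 20.6%; on Day 104, 103/364 = 28.3%.

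**Shared strains.** Protocol 6.1.1 puts B/Phuket/3073/2013 and B/Maryland/15/2016 in both 2018/2019 vaccines. SAP Tables 69 (HAI) and 73 (Neut) list the same two as 2019/2020 strains. Their Day 118 titers therefore appear against Day 1 in Tables 23–24 (HAI) and 31–32 (Neut), and against Day 90 in Tables 69 and 73.

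**What the fold rise contains.** Per subject, T118/T1 = (T90/T1) × (T118/T90), so in subjects with all three samples GMFR(1→118) = GMFR(1→90) × GMFR(90→118). For the shared strains the second factor is what the SAP reports as the response to the second vaccine. On assumed values, a 2-fold residual rise at Day 90 and a further 1- to 4-fold rise give a reported Day 118 rise of 2- to 8-fold.

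**Seroconversion under SAP 3.2 (illustration, not forecast).** B/Phuket HAI titers of 10 (Day 1), 10 (Day 90) and 40 (Day 118) give 10/10 = 1 at Day 90, so no rise remains. At Day 118, 40/10 = 4 meets the four-fold rule from Day 1 (Table 23) and again from Day 90 (Table 69).

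**Reach.** 2018/2019-strain tables are 21–68, which is 48. Those marked topline are 21–36 and 53–60: 16 + 8 = 24.

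**Sample order.** Protocol 8.5 allows the second dose before Day 76 in defined circumstances. SAP 6.3.3 accepts Visit 6 data by calendar day (75 to 105), so a sample drawn after an early dose could count as Day 90 durability. Conversely, Protocol 5.1.3 lists reasons for not giving the second dose. SAP 6.3.2 and 6.3.3 do not exclude such subjects by definition, and Table 12 gives no such reason for Days 118, 180 or 365.

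**The case against.** Several counterpoints stand.

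- The second dose is deliberate and openly stated; SAP 4.4.5 explains its timing by the recommended period for seasonal vaccination. This is not concealment. Disclosure does not, however, make later titers a measure of the first dose.
- A reader might infer that the Post Vaccination 1 heading is itself an error. It is not. The SAP uses it as a day count, including for 2019/2020 strains in Table 69 and in the implementation note for Figures 26–49. The fault lies in attributing those days to the first dose.
- SAP 8.2 names GMFR for 2018/2019 strains only at Days 57 and 90, and SAP 8.3 lists none at Days 180 and 365. Table 1 and the shells include it, so text and shells conflict. Seroconversion from Day 1 remains in both SAP sections.
- The heterologous tables (81–110) have the same post-second-dose rows, but their objectives are worded as responses, not durability. They need the interpretive note and are not counted in the 48.
- The objectives also cover kinetics and between-arm ratios. An adjuvanted arm and its unadjuvanted comparator are due the same unadjuvanted second vaccine, so the later GMT ratio remains a valid randomized comparison of sequences. To call it invalid would go too far.
- No hypothesis testing is planned for these endpoints.

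**Conclusion.** The point holds. First-dose persistence beyond about Day 90 cannot be estimated in any randomized arm, so the durability objectives at Days 118, 180 and 365, and the one-year statement, cannot be met as statements about the 2018/2019 dose alone. They can be met as descriptions of the vaccination sequence. A reader might go further and infer that reported durability will be inflated by some amount. The documents give no second-dose effect on 2018/2019 titers, so its size and direction are unknown. Day 8, Day 57 and the primary Day 29 results are unaffected; Day 90 is unaffected when drawn before the second dose, as Protocol 8.2.5 requires. The strain overlap rests on the SAP's own strain lists, and the conclusion assumes the second dose is given as scheduled. This should be corrected, but it does not threaten the primary analysis.

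**What to change.** 1. Limit the durability objectives and conclusions, and the one-year sentences in Protocol 2.2 and SAP 2, to samples drawn before the second vaccination (through Day 90).
2. Keep Days 118, 180 and 365. By a footnote or heading applied consistently across the SAP, describe them as following the scheduled 2019/2020 vaccination and as a comparison of sequences. Put the same note on Tables 81–110.
3. For 2018/2019 strains, add fold rise from the Day 90 pre-dose sample where it is not already planned. At Day 118 it already exists for the two shared B strains in the 2019/2020 HAI and Neut tables. Reconcile the GMFR days in SAP 8.2 and 8.3 with Table 1 and the shells.
4. Classify samples by their order relative to the actual second dose. Do not count a Day 90 sample drawn after an early second dose as durability. Report how many subjects did not receive the second dose, and show or flag them separately in the later rows, since a blanket label of both vaccinations would be false for them.

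Cost: wording in two objectives and four text sections, a note carried through the shells, one added fold-rise row and one sample-order rule. No new visits, samples or assays. The downside is that the stated durability period shortens to about 90 days.

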**Description of Study Design:**

This is a Phase I, randomized, double blinded, clinical trial in up to 240 males and non-pregnant females, 18-45 years of age, inclusive, who are in good health and meet all eligibility criteria. This clinical trial is designed to assess the safety, reactogenicity and immunogenicity of either the 2018/2019 Fluzone or Flublok Quadrivalent Influenza Vaccines (QIV), manufactured by Sanofi Pasteur (SP) given without adjuvant or with one of two adjuvant formulations, AF03 (SP) or Advax-CpG55.2 (Vaxine Pty Ltd). Fluzone is a quadrivalent split virion inactivated vaccine whereas Flublok is a quadrivalent influenza vaccine that contains recombinant hemagglutinin proteins. AF03 is a squalene-based emulsion adjuvant, whereas Advax-CpG55.2 is a combination adjuvant comprised of delta inulin and the oligonucleotide, CpG55.2. Enrollment will occur in the second and third quarters of calendar year 2019 to allow antibody titers to previous doses of 2018/2019 IIV to wane.

Subjects will be stratified by prior receipt of licensed, seasonal influenza vaccine (defined as receipt of at least one of the 2017/2018 and/or 2018/2019 influenza vaccines) and will be randomly assigned to 1 of 6 treatment arms to receive a single dose of one of the two seasonal 2018/2019 QIV vaccine formulations with or without one of the two adjuvants (Day 1). On approximately Day 90, each subject will receive a single dose of the seasonal 2019/2020 influenza vaccine. Groups 1, 2 and 3 will receive 2019/2020 Fluzone QIV and Groups 4, 5 and 6 will receive 2019/2020 Flublok QIV.

To determine early safety signals for this Phase I study, enrollment will proceed in a staged fashion for the first 6 sentinel subjects. The first six subjects will be randomized and vaccinated with one each from Groups 1-6. These six subjects will be followed through Day 8. If any of the pre-specified halting rules for the sentinel subjects occur, the study will be halted and reviewed by the DSMB. If no pre-specified safety signals are encountered enrollment will proceed.

It is anticipated that both adjuvant formulations (AF03 and Advax-CpG55.2) will be available at the start of study enrollment. However, if the Advax-CpG55.2 is not available, the study will proceed only with groups 1, 2, 4 and 5 open for enrollment for the remaining subjects (up to 240, 60 per group). For the sentinel subjects, one subject from groups 1, 2, 4 and 5 will be enrolled and followed through Day 8. If any of the pre-specified halting rules for sentinel subjects occur, the study will be halted and reviewed by the DSMB. If no pre-specified events occur, randomization will proceed in groups 1, 2, 4 and 5 for the remaining subjects.

The DSMB will review the data when the 8-day reactogenicity and clinical safety laboratory data following the first study vaccination are available for 50% of study

subjects. Enrollment will not be paused for this review. An additional scheduled DSMB review will occur when all HAI, NAI and Neut data for Day 1, and Day 29 and safety data through Day 57 following the first study vaccination, are available.

Reactogenicity will be measured by the occurrence of solicited injection site and systemic reactions from the time of the first study vaccination through Day 8. Unsolicited non-serious adverse events (AEs) will be collected from Day 1 through approximately Day 29. Serious adverse events (SAEs), Adverse Events of Special Interest (AESIs) including reports of tearing, dry mouth, dry eyes and medically-attended adverse events (MAAEs), including new-onset chronic medical conditions (NOCMCs) and potentially immune-mediated medical conditions (PIMMCs), will be collected from the time of study vaccination through approximately 12 months after the first study vaccination. Clinical safety laboratory evaluations (hematology and chemistry) will be performed at screening, immediately prior to the first study vaccination and at approximately Day 8.

Only pharmacy personnel, the Emmes unblinded team and an unblinded vaccinator will have access to the study codes; all other study personnel will be blinded.

Immunogenicity testing will include performing serological assays to assess hemagglutination inhibition (HAI), neutralizing (Neut) and neuraminidase inhibition (NAI) titers at multiple time points following both study vaccinations. Antibody responses will be determined for both influenza vaccine strains and heterologous influenza strains. In addition, whole blood transcriptomics and peripheral blood mononuclear cells (PBMCs) will be used to determine transcriptional profiling and broad immunologic responses and to associate these responses with serological antibody responses described above in each of the treatment arms. Immunologic responses will include longitudinal assessments of the kinetics, magnitude, specificity, and/or quality of influenza-specific memory B cells, plasmablasts, and circulating T follicular helper (TFH) cells and non-neutralizing antibody responses to HA and NA antigens

[figure not shown]
